Clinical site personnel will assess if healing of surgical wounds is sufficiently appropriate to start charging and programming of the INS. The INS will be initially programmed to the group therapy or set of stimulation parameters that provided adequate pain relief during the Trial Phase. Adjustments to therapy may be made based on patient response to a program group or set of stimulation parameters. The subject will be provided with instructions on how to operate the charger and patient remote control at this visit. Subjects will be assessed for adverse events and medication usage.

B.6.10. Unscheduled Visits

Unscheduled visits may occur at any time during the study for the assessment of possible adverse events, changes in pain medication, and programming adjustments. Each unscheduled visit will be documented and recorded on an eCRF.

B.6.11. Telephone Calls

Subjects will be contacted by the study coordinator, via a telephone call, before each study visit. The study coordinator will check on the well-being of the subject, remind the subject of the upcoming scheduled visit, remind the subject not to change pain medication usage at least two weeks prior to the scheduled visit, remind the subject not to start any new strenuous activity prior to the visit, and remind the subject to contact the Investigator/study staff should he/she have any concerns or questions. The telephone calls should be made two to three weeks *before* the scheduled visit.

B.6.12. 1 Month After Device Activation (\pm 15 days)

Subjects will visit the study site where they will be assessed for pain intensity. Programming adjustments may be made, as needed. Anterior-posterior (AP) and lateral X-ray imaging may be done if significant lead migration is suspected. Subjects will be assessed for adverse events and medication usage.

B.6.13. 3 Months After Device Activation (\pm 21 days)

Subjects will visit the study site where they will be assessed for pain intensity, extent of disability, use of medication, quality of life, Patient Global Impression of Change, and subject satisfaction. Paresthesia generated by the stimulator will be assessed. Programming adjustments may be made, as needed. Anterior-posterior (AP) and lateral X-ray imaging will be done. Subjects will also be assessed for possible adverse events and medication usage.

B.6.14. 6 Months After Device Activation (\pm 31 days)

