Remote data collection from the subjects is allowed. This should be evaluated on a case by case basis, pending Investigator's approval based on safety and clinical condition. Subjects who are not demonstrating study compliance, e.g. not returning phone calls, not charging device or turning the device off should not be mailed the questionnaires until they demonstrate compliance with the study. The site should continue to contact the subject and ensure compliance before mailing the questionnaires. The communications will be documented in the source worksheets.

Visit windows remain in place and should be maintained as much as possible. Subjects should be contacted via phone to confirm AEs, medications and concurrent procedures. All questionnaires required at a visit should be obtained via phone, email or via mail based on site and/or subject preference.

If by phone: site staff will read each question to the subject and record their answers. The site staff should initial and date the bottom of each form and indicate that it was completed via phone.

If by email: the site staff should send the provided questionnaires . Subjects can either print and manually complete or complete the forms electronically.

If manually completed (printed): the subject will be instructed to initial and date each page and scan and email or mail the responses back to the sites.

If the forms are completed electronically: the subject will be instructed to complete the questionnaires and return the responses to the site. Ideally, questionnaires will be completed and returned to the site within 3 business days.

If the questionnaires are sent in hard copy by mail: the subjects should be instructed to complete the questionnaires and initial and date each page after completion and return to site as soon as possible. Ideally, within 3 business days of receipt.

Source documentation should clearly describe the process utilized for each subject at each visit when these alternative methods are utilized.

Remote data collection/remote visits would apply to any visit that could be conducted remotely without the subject being present on-site, including remote programming, if available. Procedural visits (trial and IPG) and any unscheduled visits required for adverse events obviously should continue to be performed on-site when possible.

Table 1. Schedule of Study Activities

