Missing data will be minimized by rigorous follow-up and investigator and site training. Additionally, for subjects who do not have a successful Trial Phase, results from the Trial Phase will be utilized for the primary endpoint as described in Section B.7.2. Effectiveness Assessment Definitions. Any other data will be imputed via Multiple Imputation. Additionally, sensitivity analyses for missing data will be performed. Unless otherwise specified, all other analyses will be based on the evaluable data with no imputation.

Details on imputation will be provided in a separate statistical analysis plan.

C. Risk Analysis

C.1. Description and Analysis of All Increased Risks to Subjects

Spinal Cord Stimulation (SCS) Risks:

DTM-SCS programming approach will be used with commercially available, FDA approved Intellis™ SCS system within approved indications for use. Anticipated potential adverse events resulting from the study are expected to be in line with adverse events already documented for SCS using a Standard programming approach.

There are known risks associated with the use of any SCS system. Known risks are associated with the implant procedure, the stimulation, the implanted device (not associated with stimulation) and external devices such as the charger and remote control. These are typical of commercial SCS systems. Subjects will be informed of these anticipated risks in the study consent process.

Risks of Surgery

Implanting a neurostimulation system has risks similar to spinal procedures, including spinal fluid leak (spinal fluid collection under the skin), headaches, swelling, bruising, bleeding, infection, or paralysis.

Subjects on anticoagulation therapy may be at higher risk for problems after surgery such as hematomas that could result in paralysis.

Spinal Cord Stimulation Risks

The implantation of a spinal cord stimulation system involves risks that are similar to other spinal procedures. In addition to those normally associated with surgery, implantation or use of a neurostimulation system includes, but is not limited to the following risks:

- Allergic or immune system response to the implanted materials
- Infection
- Lead or neurostimulator erosion through the skin or migration
- Leakage of cerebrospinal fluid
- Loss of pain relief may return patients to their underlying pain condition
- Persistent pain at the neurostimulator site

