As part of the study, subjects may be required to have fluoroscopic or X-ray images taken of their thoracic spine in addition to the imaging conducted to implant the leads. This may be beyond what is standard of care. The risk associated with these additional images has been considered and determined to be minimal since the total radiation dose will be approximately the same as one CT scan of the abdomen.

Study Risk Control Measures

The following will be done to mitigate risks associated with the implanted system:

- Investigators who are experienced with spinal cord stimulation implantation techniques will be utilized
- Instructions will be given to the study participants to ensure they can properly use the patient programmer and recharger system
- Subjects can turn off stimulation at any time during the study with the patient programmer or recharger
- Periodic monitoring of the study participants
- Written materials that contain precautions, warnings, and contraindications, as well as instructions on the use of the devices will be available and/or provided to the clinicians and subjects

Since the efficacy measure in this study is intensity of pain in the back and legs, pain in these areas does not need to be reported as an adverse event unless it meets the definition of a serious adverse event. However, Investigators may, at their discretion, report any other pain-related adverse events during the study.

C2. Minimization of Risks

Neurostimulation therapies, such as SCS, are used as an aid in the management of chronic, intractable pain that cannot be effectively managed with medications and/or other conservative treatments alone. Patients considered for neurostimulation therapy have typically had pain of long duration and have failed multiple therapeutic paths.

Medtronic has carefully designed and tested the Intellis AdaptiveStim Neurostimulation Systems to ensure the safety and performance for the treatment of chronic, intractable pain. Medtronic has completed an extensive risk analysis to ensure the identification of potential hazards and subsequent mitigation of these hazards to eliminate them entirely or reduce them to an acceptable level.

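### For remote visits, B.9.1 makes mailing of outcome questionnaires depend on device use, so a month-3 VAS may be lost for reasons related to the outcome

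*Combined protocol and SAP*

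**What the plan says.** Section B.9.1 opens its remote-collection text with "Remote data collection from the subjects is allowed. This should be evaluated on a case by case basis". It then deals with subjects judged non-compliant, giving as examples those who do not return calls, do not charge the device or switch it off. Such subjects, in the words that concern device use, "not charging device or turning the device off should not be mailed the questionnaires until they demonstrate compliance with the study". A companion sentence adds: "The site should continue to contact the subject and ensure compliance before mailing the questionnaires".

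The next paragraph of B.9.1 carries no such condition: "All questionnaires required at a visit should be obtained via phone, email or via mail based on site and/or subject preference".

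Other parts of the plan that bear on this:

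- **Default visit (B.6.13).** At month 3, within a window of ±21 days, "Subjects will visit the study site where they will be assessed for pain intensity, extent of disability, use of medication, quality of life". No device-use condition is stated. Table 1 lists the VAS at month 3, also without one.
- **Freedom to switch off (C.1, Study Risk Control Measures).** "Subjects can turn off stimulation at any time during the study with the patient programmer or recharger".
- **Missing data (B.9.2.4).** The plan states that "for subjects who do not have a successful Trial Phase, results from the Trial Phase will be utilized for the primary endpoint". For the rest, "Any other data will be imputed via Multiple Imputation". Sensitivity analyses are promised but not described, imputation details are left to a separate SAP, and all other analyses default to evaluable data with no imputation.
- **Non-responder rule after implant (B.7.3).** It is triggered by a switch to programming that is neither DTM-SCS nor Conventional SCS. A device that is off or uncharged is not mentioned.

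**The concern.** The rule ties collection of a randomized subject's outcome to something that happens after randomization and is probably related to that outcome. A subject with too little relief or uncomfortable stimulation has an obvious reason to switch off or stop charging. If that subject's month-3 visit is remote and the site follows the compliance sentence, one of two things can happen. The VAS is not obtained within the window, or it is obtained only after stimulation has resumed. In both cases pain while off goes unrecorded.

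Such a subject remains in the mITT set, which B.7.1 defines as randomized subjects who complete the Trial Phase. If the VAS is missing, an imputation model that does not know the device was off will tend to give that subject values resembling those of continuing users. That raises the estimated responder rate in the arm concerned. If the arms differ in how many subjects are off, the treatment difference shifts too, and the primary test has a margin of only 10 percentage points. Results at 6 to 12 months have less protection, because missing values there are simply left out.

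**Working it through.** **1. Following an implanted, device-off subject through the plan**

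- On-site month-3 visit: VAS collected (B.6.13). No problem arises.
- Remote visit, site follows the compliance sentences in B.9.1: no form is mailed until compliance is shown.
- Remote visit, site follows the later instruction in B.9.1: the form is obtained by phone, email or mail. The two instructions give different data for the same subject.
- If no VAS is obtained: the Trial Phase rule does not apply, because the subject passed the trial, and the B.7.3 rule does not apply, because there was no switch to other programming. The value goes to Multiple Imputation (B.9.2.4).

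**2. The plan's own figure**

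B.5.5.1 gives a Farrington-Manning test, 70% v 50%, margin 10%, one-sided alpha 0.05 and 50 per group for about 90% power or more. Exact enumeration of that test at 50 per group gives power of 92.7%, so the stated size is reproduced. The same enumeration at the non-inferiority boundary, true 40% v 50%, gives a false-success rate of 4.7%.

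**3. Illustration of the effect**

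Assumptions not found in the plan: 20% of each arm are Trial Phase failures, counted as non-responders; a share f of each arm is implanted, off and without a VAS; all of these are true non-responders; they are imputed at the responder rate of the other implanted subjects; the extra variance from Multiple Imputation is ignored.

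True responders are a share p of the arm, and all of them are among the observed implanted subjects, a share 1 − 0.20 − f. Hence

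expected rate = p + f × p / (1 − 0.20 − f)

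For 8% Test and 2% Control off:

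- Test: 0.40 + 0.08 × 0.40 / 0.72 = 44.4%
- Control: 0.50 + 0.02 × 0.50 / 0.78 = 51.3%
- Apparent difference −6.8 points against a true −10, a shift of 3.2 points.

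Putting each pair of rates back into the exact enumeration (50 per arm):

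| Off: Test v Control | Expected rates | Apparent difference | False success |
|---|---|---|---|
| none | 40.0% v 50.0% | −10.0 | 4.7% |
| 8% v 2% | 44.4% v 51.3% | −6.8 | 8.5% |
| 5% v 3% | 42.7% v 51.9% | −9.3 | 5.3% |
| 4% v 4% | 42.1% v 52.6% | −10.5 | 4.1% |
| 2% v 8% | 41.0% v 55.6% | −14.5 | 1.6% |

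Both estimated responder rates rise in every row with subjects off. The error rate of the test rises or falls according to which arm loses more.

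**The case against.** The case against is substantial, and much of it stands.

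- **Scope.** The condition sits in an optional, case-by-case remote procedure and names mailing only. On-site month-3 visits carry no such condition, and phone and email are listed routes. This stands. A reader might infer that the plan withholds questionnaires in general, or that outcomes will come mainly from continuing users. The documents do not support either reading, because they give neither the share of remote visits nor the device-off rate. What remains is that the intent to hold back remote questionnaires is plain and conflicts with the later instruction.
- **A hold, not an exclusion.** Sites are to keep contacting the subject, so the form may still arrive. This stands too, but the hold can outlast the ±21-day window, or end only once the subject is using the device again.
- **Therapy failures.** It is tempting to say that failures in general are left to imputation. They are not. The synopsis counts Trial Phase failures as non-responders, and B.7.2 assesses them, and those who decline implant for insufficient relief, at the end of the Trial Phase. Only failures after implant are exposed.
- **Imputation.** The details are in a separate SAP that was not available. End-of-trial and month-1 VAS could inform the model, so imputing at the average rate of other implanted subjects is a pessimistic assumption.
- **Direction.** A reader might infer that the rule favours a finding of non-inferiority. That requires more subjects off in the Test arm, and nothing in the plan says so. B.1 suggests that DTM-SCS may cause less uncomfortable stimulation than Conventional SCS, which would point the other way.

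**Conclusion.** The concern holds in a limited form. B.9.1 contains conflicting instructions on collecting outcomes at remote visits, and one of them makes collection depend on device use after randomization. For implanted subjects no scoring rule fills the gap, so a month-3 VAS lost this way is likely to be informatively missing. It is then imputed for the primary analysis and ignored in the analyses that use evaluable data.

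The size cannot be determined from the documents. In the illustration, false success ranges from 1.6% to 8.5% against 4.7% with nobody off, and stays close to 4.7% when the arms are similar (5.3% and 4.1%). These figures assume the off-rates, assume that every such subject is a true non-responder reached by no route, and assume an uninformative imputation model. They show that the test is sensitive to an imbalance between arms; they do not predict a bias, and its direction is unknown. This is a should-fix: the exposure is unquantified, but a month-3 score that is not collected cannot be recovered later and the remedy is cheap.

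**What to change.** 1. In B.9.1, delete the sentence that makes mailing conditional on compliance, and its companion about ensuring compliance first.
2. Replace them with a statement that all visit questionnaires are sent or administered at every scheduled visit, by any allowed route, to every subject who has not withdrawn consent, whether or not the device is charged, on or in use.
3. Record device-off or not-charging status at each visit as a separate item, so that it can enter the imputation model if the VAS is still missing.
4. Add to B.9.2.4 and the SAP a sensitivity analysis of the primary endpoint that counts device-off subjects with a missing month-3 VAS as non-responders.

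The cost is a short amendment, one added data item, one added analysis and site retraining. Some VAS scores will come from subjects who are off stimulation, so the observed responder rate may be slightly lower.
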